**NOTE 2:**

- **The durvalumab dose of 1500 mg Q4W is for subjects > 30 kg.** If a subject's body weight drops to ≤ 30 kg while on the study, the subject will receive weight-based dosing equivalent to 20 mg/kg of durvalumab as long as the body weight remains ≤ 30 kg (e.g., a 30 kg subject would receive a 600 mg dose; a 25 kg subject would receive a 500 mg dose; etc.). When the weight improves to >30 kg, the subject may return to fixed dosing of durvalumab 1500 mg.
- **When tremelimumab 75 mg Q4W (x4) is given with durvalumab 1500 mg Q4W,** if a subject's body weight drops to ≤ 30 kg while on the study, the subject will receive weight-based dosing for both drugs. For durvalumab, the weight-based dosing is described above; for tremelimumab, weight-based dosing equivalent to 1 mg/kg tremelimumab will be given as long as the body weight remains ≤ 30 kg (e.g., a 30 kg subject would receive a 30 mg dose; a 25 kg subject would receive a 25 mg dose; etc.). When the weight improves to >30 kg, the subject may return to fixed dosing of tremelimumab 75 mg and durvalumab 1500 mg.

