#### 3.1.7.1 Dose Evaluation Phase

Each subject enrolled in the dose evaluation cohorts of the study will be evaluated for dose-limiting toxicities (DLTs), as defined in Section 3.1.9. Dose de-escalation and evaluation of RCD will be performed based on the available dose levels (see table below) and the respective rules for a standard 3 + 3 study design (see Schema below).

For Arm A, the RCD of BI 1361849 + durvalumab is determined. The starting dose of durvalumab is 1500 mg with possible de-escalation to 750 mg; the dose for BI 1361849 remains constant. For Arm B, the RCD of BI 1361849 + durvalumab from Arm A with the addition of tremelimumab 75 mg is evaluated. There is no dose escalation/de-escalation for Arm B; if there is unacceptable toxicity in Arm B, the arm will be discontinued.

Dose Level Table for Evaluation Phase						
Dose Level	Arm A		Dose Level	Arm B*		
	BI 1361849	Durvalumab		BI 1361849	Durvalumab	Tremelimumab
-1	12 x 80 µg**	750 mg				
Starting	12 x 80 µg**	1500 mg	Starting	12 x 80 µg**	RCD from Arm A	75 mg

[figure not shown]
\*If there is unacceptable toxicity in Arm B, dosing will continue at RCD from Arm A, without tremelimumab.

\*\*BI 1361849 is a vaccine comprising six drug product components (F2408, F2409, F2410, F2624, F2625, and F2626), which are provided and administered separately; each component is administered twice, thus there are 12 administrations of 100 µL (80 µg) each.

**NOTE 1:** The Pharmajet Tropis® device will be used for the administration of the BI 1361849 components. Allowing for a filling volume of 100 µL (80 µg) and 2 administrations per component, the recommended dose per each of the 6 antigen components will be 160 µg (2 x 80 µg), for a total of 960 µg (12 administrations). See Section 6.3.3 for details on the administration of BI 1361849.

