#### 6.1.3 Durvalumab Preparation

The dose of durvalumab for administration must be prepared by the IP manager or designated personnel using aseptic technique. No incompatibilities between durvalumab and polyvinylchloride or polyolefin copolymers have been observed.

CONFIDENTIAL

Dose Calculation:

Subjects will receive a fixed dose of durvalumab:

- **Starting dose:1500 mg Q4W**

NOTE: the durvalumab dose of 1500 mg Q4W is for subjects > 30 kg. If a subject's body weight drops to ≤ 30 kg while on the study, the subject will receive weight-based dosing equivalent to 20 mg/kg of durvalumab as long as the body weight remains ≤ 30 kg (e.g., a 30 kg subject would receive a 600 mg dose; a 25 kg subject would receive a 500 mg dose; etc.). When the weight improves to >30 kg, the subject may return to fixed dosing of durvalumab 1500 mg.

- **Dose de-escalation: 750 mg Q4W**

The volume of durvalumab (in mL) to be added to the IV bag is calculated as follows:

Volume of Durvalumab (mL)	=	Dose level (mg)	÷	Durvalumab Concentration (nominal 50 mg/mL)
---------------------------	---	-----------------	---	---

Dose Preparation:

Durvalumab will be administered using an IV bag containing 0.9% (w/v) saline or 5% (w/v) dextrose and delivered through an IV administration set with a 0.2 or 0.22 µm in-line filter. The final durvalumab concentration after dilution in the bag must be 1 mg/mL to 15 mg/mL. The calculated volume of durvalumab is added to the IV bag, and the bag is mixed by gentle inversion to ensure homogeneity of the dose in the bag.

*Example:* For a 1500 mg dose (for subjects > 30 kg in weight), 30 mL of durvalumab may be diluted in a 250 mL IV bag, and the bag is mixed by gentle inversion.

Durvalumab does not contain preservatives; any unused portion must be discarded.

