### 2.3 Trial Design and Trial Procedures

This is an open-label multicenter 2-arm study to evaluate the safety and preliminary efficacy of the addition of a vaccine therapy to 1 or 2 checkpoint inhibitors for NSCLC:

- Arm A: mRNA Vaccine [BI 1361849 (formerly CV9202)] + anti-PD-L1 [durvalumab].
- Arm B: mRNA Vaccine [BI 1361849] + anti-PD-L1 [durvalumab] + anti-CTLA-4 [tremelimumab].

For each arm of the study, there is a *dose evaluation phase* in which the Recommended Combination Dose (RCD) is determined according to a standard 3 + 3 design. For Arm A, the RCD of BI 1361849 + durvalumab is determined. The starting dose of durvalumab is 1500 mg with possible de-escalation to 750 mg; the dose for BI 1361849 remains constant at 12 x 80 ug. The 1500 mg Q4W dosing of durvalumab is recommended only for subjects with > 30kg body weight. Subjects with a body weight  $\leq$  30 kg are not eligible for enrollment in the current study. If a subject's body weight drops to  $\leq$  30 kg while on the study, the subject will receive weight-based dosing equivalent to 20 mg/kg of durvalumab as long as the body weight remains  $\leq$  30 kg. When the weight improves to >30 kg, the subject may return to fixed dosing of durvalumab 1500 mg.

[figure not shown]
For Arm B, the RCD of BI 1361849 + durvalumab from Arm A with the addition of tremelimumab 75 mg is evaluated. There is no dose escalation/de-escalation for Arm B; if there is unacceptable toxicity in Arm B, the arm will be discontinued as presented in Figure 1.

The *dose evaluation phase* is followed by an *expansion phase*, in which the cohort at the RCD for each arm is expanded to 20 subjects (inclusive of the subjects from the dose evaluation cohort i.e., 14 subjects will be added to the 6 treated at the RCD in the dose evaluation phase for each arm (A and B).

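### Because the weight rule covers only durvalumab 1500 mg, a subject who falls to 30 kg or less gets a larger single durvalumab dose at the de-escalated level than at the starting level

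*Protocol*

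**What the plan says.** Protocol 3.1.7.1 sets the two durvalumab levels for Arm A: "The starting dose of durvalumab is 1500 mg with possible de-escalation to 750 mg". Arm B takes whichever durvalumab dose Arm A settles on and adds tremelimumab 75 mg.

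NOTE 2 of the same section deals with subjects whose weight falls to 30 kg or less on study.
- **Durvalumab.** The rule opens with "The durvalumab dose of 1500 mg Q4W is for subjects > 30 kg" and then calls for "weight-based dosing equivalent to 20 mg/kg of durvalumab" while weight stays at or below 30 kg. The worked example is that "a 30 kg subject would receive a 600 mg dose". Once weight recovers, "the subject may return to fixed dosing of durvalumab 1500 mg". No other return dose is given.
- **Tremelimumab.** The rule of 1 mg/kg at or below 30 kg is introduced by "When tremelimumab 75 mg Q4W (x4) is given with durvalumab 1500 mg Q4W".

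Protocol 6.1.3 (durvalumab preparation) places the weight note under the starting dose and then lists "Dose de-escalation: 750 mg Q4W" with no weight note. Protocol 6.2.3 (tremelimumab preparation) repeats the restriction to use with durvalumab 1500 mg. The Amendment 5 entry in Protocol 8.1 describes this scope as an intended clarification.

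Protocol 2.2 recommends durvalumab 1500 mg and tremelimumab 75 mg for subjects above 30 kg, and gives endotoxin exposure as the reason for the durvalumab limit. The Synopsis sends the reader to 3.1.7.1 for doses at or below 30 kg, under a table that lists both durvalumab levels.

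**The concern.** De-escalation is meant to lower the durvalumab dose. For a subject at or below 30 kg the stated rules do the opposite: the starting level drops to a weight-based dose, while the de-escalated level stays at 750 mg, which is above that weight-based dose.

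A second difficulty concerns Arm B. Whether a subject at or below 30 kg receives a reduced tremelimumab dose depends on which durvalumab dose Arm A produced, not on the subject's weight alone. With an RCD of 750 mg the subject would stay on 75 mg, a dose that Protocol 2.2 recommends for subjects above 30 kg.

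What is at stake is the dose given to a few light subjects, and whether a site can see why it differs between levels. The primary endpoints are not at stake.

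**Working it through.** **Inputs**
- Durvalumab levels: 1500 mg and 750 mg, fixed (Protocol 3.1.7.1, dose table).
- Weight rules at or below 30 kg: durvalumab 20 mg/kg and tremelimumab 1 mg/kg, both only with durvalumab 1500 mg (3.1.7.1 NOTE 2; 6.1.3; 6.2.3).
- Tremelimumab fixed dose: 75 mg (3.1.7.1).
- Entry weight: above 30 kg (5.1, criterion 10).
- DLT Evaluation Period: the first two cycles, up to the pre-dose assessment of Cycle 3 (3.1.9). This contains two durvalumab doses, on Day 1 of Cycles 1 and 2 (3.1.7).

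**The protocol's own examples.** Dose = mg/kg × weight.
- Durvalumab: 20 × 30 = 600 mg; 20 × 25 = 500 mg.
- Tremelimumab: 1 × 30 = 30 mg; 1 × 25 = 25 mg.

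All four match NOTE 2.

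**Single durvalumab dose, 750 mg level against 1500 mg level**

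| Weight | 1500 mg level | 750 mg level | Ratio |
|---|---|---|---|
| 30 kg | 600 mg | 750 mg | 750/600 = 1.25 |
| 25 kg | 500 mg | 750 mg | 750/500 = 1.5 |

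A fixed 750 mg exceeds 20 mg/kg at every weight below 750/20 = 37.5 kg. The reversal therefore covers the whole range in which the weight rule operates. Above 30 kg the order is as intended, 750 mg against 1500 mg.

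**Tremelimumab in Arm B, by Arm A RCD**

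| Weight | RCD 1500 mg | RCD 750 mg | Ratio |
|---|---|---|---|
| 30 kg | 30 mg | 75 mg | 75/30 = 2.5 |
| 25 kg | 25 mg | 75 mg | 75/25 = 3 |

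**Does the reversal reach the DLT comparison?** Assume the first dose is given above 30 kg, as entry requires, and take the extreme case in which weight has fallen by Cycle 2 Day 1. Cumulative durvalumab in the DLT period is then:
- 750 mg level: 750 + 750 = 1500 mg.
- 1500 mg level at 30 kg: 1500 + 600 = 2100 mg.
- 1500 mg level at 25 kg: 1500 + 500 = 2000 mg.

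In general the starting level gives 1500 + 20 × weight, which always exceeds 1500 mg. The DLT period is not reversed.

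**When would cumulative totals cross?** With weight constant from the second dose on, after n doses:
- At 30 kg: 750n > 1500 + 600(n − 1), so 150n > 900 and n > 6.
- At 25 kg: 750n > 1500 + 500(n − 1), so 250n > 1000 and n > 4.

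The crossing comes after the DLT period in both cases.

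**The case against.** The strongest defence is that the scope is deliberate. The Amendment 5 log says so, Protocol 3.1.7.1, 6.1.3 and 6.2.3 agree with one another, and Protocol 2.2 gives a reason: endotoxin exposure at 1500 mg. Whether 750 mg needs a weight rule on that ground depends on endotoxin data that the documents do not contain. This stands as an explanation of why 750 mg was left out. It does not remove the reversal in the durvalumab dose, and it does not explain why the tremelimumab rule should depend on the durvalumab level.

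Four stronger readings are tempting, and the documents do not support them.
- **De-escalated DLT data would not reflect a lower dose.** A reader might infer this from the single-dose ratios. The cumulative check shows otherwise for the DLT period. DLTs outside it may also influence decisions under Protocol 3.1.9, but the decisions rest primarily on that period.
- **The SAP contradicts the protocol and would double the assigned level.** SAP 2.3 says "When the weight improves to >30 kg, the subject may return to fixed dosing of durvalumab 1500 mg". Read alone, that could seem to move a 750 mg subject to 1500 mg. The sentence follows directly on a statement about 1500 mg dosing, and a return presupposes that the subject was on 1500 mg before. It can be read with the same limit as NOTE 2.
- **Tremelimumab is raised at the de-escalated level.** That level exists only in Arm A, which has no tremelimumab. Arm B has a single level, so no Arm B dose order is broken. The tremelimumab point compares two possible Arm A outcomes.
- **The overdose definition cannot be applied.** Protocol 6.6 measures excess over the dose that the protocol specifies, and at the de-escalated level that dose is 750 mg throughout. The supposed ambiguity needs the SAP reading rejected above.

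**Conclusion.** The point holds in a limited form. As the protocol stands, a subject at or below 30 kg receives a single durvalumab dose 1.25 times (30 kg) to 1.5 times (25 kg) as large at the 750 mg level as at the 1500 mg level. With an Arm A RCD of 750 mg, an Arm B subject at or below 30 kg would receive 2.5 to 3 times the tremelimumab dose that applies with an RCD of 1500 mg, and this does not fit the weight statement in Protocol 2.2.

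The conclusion rests on reading the weight rule as confined to 1500 mg. The wording of NOTE 2, the single return dose and the Amendment 5 log all favour that reading. If the 20 mg/kg rule were instead applied at both levels, the durvalumab dose at 30 kg would be 600 mg at each. De-escalation would then make no difference for these subjects.

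The practical weight is low. The point needs weight loss on study to 30 kg or less and use of the 750 mg level, and the documents show neither. It is worth correcting because it bears on subject safety and costs little.

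**What to change.** The sponsor should reconcile Protocol 2.2, 3.1.7.1 (dose table and NOTE 2), 6.1.3 and 6.2.3, and align SAP 2.3. For each durvalumab level the text should state what a subject at or below 30 kg receives and what dose applies once weight recovers. For tremelimumab it should state this for either possible Arm A RCD. The statements should be consistent with the de-escalation order and with the weight statement in Protocol 2.2, or the protocol should give the reason for any difference. SAP 2.3 should name the level to which its weight rule applies.

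Which doses apply is for the sponsor to decide, and none is proposed here. The cost is a clarifying sentence or two per drug in the protocol and a matching sentence in the SAP. No analysis, sample size or endpoint changes.

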**Figure 2. Dose Escalation and De-Escalation Schema**

Per Figure 2, the RCD for Arm A and Arm B is defined as the highest dose level at which no more than 1 of 6 subjects (i.e., < 33%) experience DLTs. The RCD cannot be determined if none of the predefined dose level cohorts fulfill that criterion. In such case, the arm will be discontinued without an expansion phase.

### 3.1.7.2 Dose Expansion Phase

In each arm for which an RCD is declared in the dose evaluation phase, the RCD dose level cohort will be expanded to 20 subjects (i.e., 14 subjects will be added to the 6 treated at the RCD in the dose evaluation phase for each arm (A and B)).

### 3.1.8 Dosing Adjustments, Delays, and Discontinuations

Individual subject dosing adjustments due to toxicity will be allowed/may be required in accordance with the “Dose Adjustment and Management Guidelines” for toxicity related to durvalumab / tremelimumab and BI 1361849, outlined in Section 8.3 and Section 8.4, respectively.

If a toxicity occurs that requires toxicity management in accordance with Sections 8.3 or 8.4, and the toxicity causing drug can be clearly identified, then the respective guideline should be followed. If the toxicity causing drug cannot be identified, then the more conservative guideline should be followed.

### 3.1.9 DLT and MTD/RCD for the Combination Therapy

MTDs will not be determined in this study. Instead, RCDs will be determined in the context of the predefined dose levels used during the dose evaluation phase as per Section 3.1.7.1.

DLTs will be observed over a period of the first 2 cycles of the combination therapy, including the pre-dose assessment for Cycle 3, defined as the **DLT Evaluation Period**. The decisions for dose evaluations, de-escalations and RCD, as described in Section 3.1.7.1 will primarily be based on the number of subjects with DLTs occurring during the DLT Evaluation Period. DLTs occurring outside the DLT Evaluation Period will also be evaluated and may impact such decisions.

DLTs are defined as any adverse events that are possibly, probably, or definitely related to the administration of durvalumab, tremelimumab, or BI 1361849 components, and fulfill any of the following criteria:

1. Any Grade  $\geq 3$  colitis, pneumonitis, neurological event or uveitis.
2. Any Grade 2 pneumonitis, neurological event or uveitis, with the following exception:
  - Grade 2 pneumonitis, neurological event or uveitis that downgrade to Grade  $\leq 1$  within 3 days after onset, whereby maximal supportive care, including systemic corticosteroids, is permitted.
3. Any *other* Grade  $\geq 3$  toxicity, with the following exceptions:
  - Grade 3 irAEs that downgrade to Grade  $\leq 2$  within 3 days, or to Grade  $\leq 1$  or baseline within 14 days after onset, whereby maximal supportive care, including systemic corticosteroids, is permitted.
  - Grade 3 endocrinopathy that becomes asymptomatic when managed with or without systemic corticosteroid therapy and/or hormone replacement therapy.
  - Grade 3 inflammatory reaction attributed to a local antitumor response (e.g., inflammatory reaction at sites of metastatic disease, lymph nodes, etc.).
  - Grade 3 fatigue for  $\leq 7$  days.
  - Grade 3 infusion-related reaction (first occurrence and in the absence of steroid prophylaxis) that resolves within 6 hours with appropriate clinical management.
  - Liver transaminase elevation  $\leq 8$  times ULN that downgrades to Grade  $\leq 2$  ( $\leq 5$  times ULN) within 7 days after onset, whereby maximal supportive care, including systemic corticosteroids, is permitted.
  - Total bilirubin  $\leq 5$  times ULN that downgrades to Grade  $\leq 2$  ( $\leq 3$  times ULN) within 7 days after onset, whereby maximal supportive care, including systemic corticosteroids, is permitted.
  - Grade  $\geq 3$  neutropenia that (1) is not associated with fever or systemic infection, (2) does not require medical intervention, and (3) improves to Grade 2 within 7 days.
  - Grade 3 and 4 lymphopenia.
  - Grade 3 thrombocytopenia that (1) is not associated with clinically significant bleeding, (2) does not require medical intervention, and (3) improves to Grade 2 within 7 days.
  - Isolated Grade 3 electrolyte abnormalities that are not associated with clinical signs or symptoms and are reversed with appropriate maximal medical intervention within 3 days.
  - Any pre-existing laboratory abnormality that deteriorates to Grade 3/4, but where the increment of deterioration is considered not clinically significant by both investigator and sponsor.
  - Grade 3 or 4 asymptomatic increases in amylase or lipase levels for which appropriate evaluation shows no clinical evidence of pancreatitis.

Immune-related AEs (irAEs) are defined as AEs of immune nature (i.e., inflammatory) in the absence of a clear alternative etiology. In the absence of clinical abnormality, repeat laboratory testing will be conducted to confirm significant laboratory findings prior to designation as a DLT.

While rules for adjudicating DLTs are specified above, an AE that is Grade < 3 or listed as exempt above may also be defined as DLT after consultation with the sponsor and Investigators, based on the emerging safety profiles of durvalumab, tremelimumab, and BI 1361849. Likewise, subjects who become not evaluable for DLT, because they discontinued or interrupted treatment due to toxicities other than DLTs, may be counted as DLT subjects, if the toxicities cannot be managed in accordance with the dosing modifications described in Section 3.1.8.

Subjects who experience a DLT will be discontinued from study treatment and will enter the On Study and Post Study Follow-up (see Section 3.1.16). However, if it is in the best interest of the subject, the Investigator, subject and Sponsor may agree to continue treatment with BI 1361849.

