A consult with a Nephrologist should be done as well as monitoring for signs and symptoms that may be related to changes in renal function (e.g., routine urinalysis, elevated serum BUN and creatinine, decreased creatinine clearance, electrolyte imbalance, decrease in urine output, proteinuria, etc.). Subjects should be thoroughly evaluated to rule out any alternative etiology (e.g., disease progression, infections, etc.). Steroids should be considered in the absence of clear alternative etiology even for low grade events (Grade 2), in order to prevent potential progression to higher grade event.
- **Pancreatic Disorders**  
Immune-mediated pancreatitis includes autoimmune pancreatitis or labs suggestive of pancreatitis (increased serum lipase, increased serum amylase).
- **Myocarditis**  
Myocarditis, a rare, but severe immune-mediated adverse event, presents with signs/symptoms such as decreased ejection fraction, arrhythmias, in particular occurrences of atrioventricular block. For patients with suspected myocarditis, investigators should obtain a cardiology consult and institute full diagnostic work-up (that includes exclusion of other alternate causes such as infection).
- **Myositis /Polymyositis**  
Myositis or polymyositis should be suspected in patients who present with proximal muscle weakness and the evaluation should include an examination of the skin, muscle enzyme measurement, antibody testing, any systemic disease manifestations and exclusion of other diseases including drug-induced myopathy. Cases of myositis have been reported with myocarditis in which immune infiltration has been described in skeletal and cardiac muscle (see IB).
- **Other inflammatory responses** that are rare / less frequent with a potential immune-mediated aetiology include, but are not limited to, pericarditis, sarcoidosis, uveitis, and other events involving the eye, skin, haematological and rheumatological events.
- **Hypersensitivity and Infusion Reactions**

CONFIDENTIAL

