#### 8.3.1 Durvalumab and Tremelimumab Dose Modification Due to Toxicity

Durvalumab (MEDI4736) and tremelimumab administration may be modified or discontinued as a result of toxicities as described in the table below.

Additional information and guidance regarding dose modification due to toxicity are provided from Medimmune in the following guidelines:

***“Medimmune’s Dosing Modification and Toxicity Management Guidelines for Immune-mediated, Infusion Related, and Non Immune-mediated Reactions (MEDI4736 (durvalumab) Monotherapy or Combination therapy with Tremelimumab or Tremelimumab monotherapy).”***

Dose modifications will not be required for AEs that are clearly not attributed to durvalumab or tremelimumab (such as an accident) or for laboratory abnormalities that are not deemed to be clinically significant.

MEDI4736 (M) and Tremelimumab (T) Dose Modification Due to Toxicity
Note: If M and T dosing is held temporarily until resolution of the event as per instructions below, treatment should resume at the next scheduled treatment date.
Immune-related Adverse Events (irAEs) Immune-related adverse events are defined as AEs of immune nature (i.e., inflammatory) in the absence of a clear alternative etiology. Maximum supportive care, including immunosuppressive medications, such as high dose steroids, is allowed to induce resolution of the event. However, infliximab should not be used for management of immune-related hepatitis. In addition to the criteria for permanent discontinuation of M and T depicted below, permanently discontinue M and T also for: 

• Any Grade rash with bullous skin formations.

• Inability to reduce corticosteroid to a dose of <math>\leq 10</math> mg of prednisone per day (or equivalent) within 12 weeks after last dose of study drug/regimen.

• Recurrence of a previously experienced Grade 3 treatment-related AE following resumption of dosing.

• Any Grade biopsy-proven immune-mediated myocarditis.

 Grade 1 

• In general, no dose modification required.

• For pneumonitis/interstitial lung disease and myocarditis, consider holding M and T dosing as clinically appropriate and during diagnostic work-up for other etiologies.

CONFIDENTIAL

## Grade 2

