- In general, hold M and T until resolution to  $\leq$  Grade 1 and after the end of any steroid taper, and discontinue M and T permanently if such resolution does not occur within 60 days (30 days for neurotoxicities). Criteria for temporary hold or permanent discontinuation of M and T may differ by event as detailed below.
- For *myositis/polymyositis*, hold M and T until resolution to  $\leq$  Grade 1; permanently discontinue M and T if it does not resolve to  $\leq$  Grade 1 within 30 days or if there are signs of respiratory insufficiency.
- For *pneumonitis/interstitial lung disease and myocarditis*, the decision to reinitiate M and T upon resolution shall be based upon treating physician's clinical judgment (as long as the event does not meet DLT criteria).
- For *peripheral neuromotor syndromes*, such as *Guillain-Barre* and *Myasthenia Gravis*, follow general instructions above, but always discontinue M and T permanently if there are signs of respiratory insufficiency or autonomic instability.
- For *endocrinopathies, other than isolated hypothyroidism and isolated Type 1 diabetes mellitus*, follow general instructions above, but subjects may be retreated if the endocrinopathy is controlled and the subject is clinically stable while requiring steroid doses of  $\leq$  10 mg/day prednisone equivalent.
- For *isolated hypothyroidism* managed with hormone replacement therapy, *isolated Type 1 diabetes mellitus* treated with appropriate diabetic therapy, and for *sensory neuropathy/neuropathic pain*, holding M and T is at the discretion of the Investigator.
- For *elevated creatinine* or *rash*, M and T should be held until resolution to  $\leq$  Grade 1 or baseline and after completion of steroid taper.
- For *vitiligo*, no dose modification required.

## Grade 3

- In general, hold M and T until resolution to  $\leq$  Grade 1, and after the end of any steroid taper, and discontinue M and T permanently if such resolution does not occur within 60 days (30 days for neurotoxicities and rash). Criteria for permanent discontinuation of M and T may differ by event as detailed below.
- For *myositis/polymyositis*, follow Grade 2 instructions above.
- For *peripheral neuromotor syndromes* (such as *Guillain-Barre* and *Myasthenia Gravis*), apply respective Grade 2 rules.
- For *endocrinopathies*, follow Grade 2 instructions above.
- For *diarrhea/colitis*, permanently discontinue M and T if toxicity does not improve to  $\leq$  Grade 1 within 14 days.

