- For *pneumonitis/interstitial lung disease, myocarditis, and elevated serum creatinine (e.g., nephritis or renal dysfunction)*, always discontinue M and T permanently.
- For *asymptomatic increases of amylase or lipase* levels, hold M and T, and if complete work up shows no evidence of pancreatitis, M and T may be continued.
- For *hepatitis*, discontinue M and T permanently for (1) transaminases or bilirubin not resolving to  $\leq$  Grade 1 or baseline within 14 days, (2) transaminases  $> 8 \times$  the upper limit of normal (ULN) or bilirubin  $> 5 \times$  ULN, or (3) any case meeting Hy's law criteria (as defined in FDA Guidance Document "Drug-Induced Liver Injury").
- For *rash*, M and T should be held until resolution to  $\leq$  Grade 1 or baseline.

CONFIDENTIAL

MEDI4736 (M) and Tremelimumab (T) Dose Modification Due to Toxicity

Grade 4
 
 
• In general, discontinue M and T permanently.
 
• For endocrinopathies, follow Grade 2 instructions above.
 
• For asymptomatic increases of amylase or lipase levels, hold M and T, and if complete work up shows no evidence of pancreatitis, M and T may be continued.
 

Infusion-related Reactions
 
Grade 1
 
 
• The infusion rate of M and T may be decreased 50% or temporarily interrupted until resolution of the event.
 
• Acetaminophen and/or antihistamines may be administered per institutional standards at the discretion of the Investigator.
 
• Premedication for subsequent doses should be considered.
 
• Steroids should not be used for routine premedication of <math>\leq</math>Grade 2 infusion reactions
 
 
Grade 2:
 
 
• Same as Grade 1, but consider giving subsequent infusions at 50% of the initial infusion rate.
 
 
Grade 3 and 4:
 
 
• The infusion must be stopped immediately and treatment permanently discontinued.
 
• Manage severe infusion-related reactions per institutional standards (e.g., IM epinephrine, followed by IV diphenhydramine and ranitidine, and IV glucocorticoid).
 

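### A Grade 3 immune myocarditis or nephritis that downgrades in time stops both antibodies permanently under Protocol 8.3.1, yet by default is not a DLT under 3.1.9

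*Protocol*

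**What the plan says.** **When treatment stops.** In Protocol 8.3.1 one Grade 3 bullet for immune-related events covers "pneumonitis/interstitial lung disease, myocarditis, and elevated serum creatinine (e.g., nephritis or renal dysfunction"). Both antibodies are then always stopped for good. Two other rules there single out myocarditis. "Any Grade biopsy-proven immune-mediated myocarditis" is a permanent stop. After Grade 2 pneumonitis or myocarditis, restart is left to the physician "as long as the event does not meet DLT criteria". The introduction to 8.3.1 waives dose modification for laboratory abnormalities that are not clinically significant, which qualifies the rule for creatinine.

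**What counts as a DLT.** Criterion 1 of Protocol 3.1.9 makes related Grade 3 or higher "colitis, pneumonitis, neurological event or uveitis" a DLT without exception. Every other related Grade 3 or higher toxicity falls under criterion 3. The first exception there is "Grade 3 irAEs that downgrade to Grade" 2 or lower within 3 days, or to Grade 1 or lower "or baseline within 14 days after onset, whereby maximal supportive care, including systemic corticosteroids, is permitted".

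**Discretion.** Under 3.1.9, an event "listed as exempt above may also be defined as DLT after consultation with the sponsor and Investigators". A second clause allows a non-evaluable subject who stopped for other toxicity to be counted, if the toxicity cannot be managed under 3.1.8.

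**Evaluability and decision.** Under 4.1.2, a subject without a DLT needs at least 75% of the antibody doses and 4 of the 5 vaccinations in the DLT period. Others are replaced (mandatory in Protocol 3.1.11, optional in SAP 11.1). Under 3.1.7.1, the RCD allows at most 1 of 6 subjects with a DLT. A pass opens the level to 14 more subjects per arm.

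**The concern.** Three events share one mandatory stop, but only pneumonitis is certain to enter the DLT count. A subject taken off both antibodies for good because of related Grade 3 myocarditis or nephritis can leave no trace in the count that sets the RCD. DLTs and the RCD are primary endpoints of the dose evaluation phase.

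The Grade 2 rule in 8.3.1 points the same way. It makes restart after myocarditis depend on the DLT criteria, but criterion 2 of 3.1.9 does not list Grade 2 myocarditis. For myocarditis, only the discretionary clause could make that condition bite.

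Neither document requires anyone to decide whether such an event counts. The SAP plans no alternative DLT count that would show whether the RCD decision depended on it.

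**Working it through.** **1. The plan's own threshold.** 1/6 = 16.7% passes; 2/6 = 33.3% fails. This agrees with the limit in 3.1.7.1 (no more than 1 of 6, below 33%).

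**2. Which events fall in the gap.** They must be related, immune-mediated and Grade 3, must be myocarditis or clinically significant creatinine elevation/nephritis, and must downgrade within the 3-day or 14-day limit. Grade 4 events and Grade 3 immune events that do not downgrade in time remain DLTs in general.

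**3. What happens to the subject by default.** From the dosing table in 3.1.7, the DLT period (Cycles 1 and 2) has antibody dosing on Days 1 and 29 and vaccination on Days 1, 8, 15, 29 and 43.

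- Stopped before the Cycle 2 dose: antibody doses 1/2 = 50%, below 75%. The subject is not evaluable and is replaced.
- Stopped after a complete Cycle 2 Day 1 visit: antibody doses 2/2 = 100% and vaccinations at least 4/5 if none was missed. With the required assessments and no major violation, the subject is evaluable and scored as no DLT.

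**4. One cohort of six.** Suppose one subject is affected and one of the other five has a DLT.

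- Affected subject counted: 2/6, the level fails.
- Scored as no DLT: 1/6, the level passes.
- Replaced: the level passes if the replacement has no DLT, a probability of 80% to 95% for an assumed DLT rate of 20% down to 5%.

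**5. Chance of passing, given one affected subject.** Let p be the assumed rate of other DLTs, with independent subjects. Pass means at most 1 DLT in 6. Stopping early at 2 DLTs in the first 3 does not change this probability.

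| p | Counted: (1−p)^5 | Replaced: P(Bin(6,p) ≤ 1) | Scored as no DLT: P(Bin(5,p) ≤ 1) |
|---|---|---|---|
| 5% | 0.774 | 0.967 | 0.977 |
| 10% | 0.590 | 0.886 | 0.919 |
| 15% | 0.444 | 0.776 | 0.835 |
| 20% | 0.328 | 0.655 | 0.737 |

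**6. Unconditional effect.** Let q be the chance per subject of an event in the gap. The documents give no rate, so a range is shown. If the events are counted and are independent of other DLTs, the rate per subject is r = 1 − (1−p)(1−q), and P(pass) = (1−r)^6 + 6r(1−r)^5. If they are ignored at p = 10%, P(pass) = 0.9^6 + 6 × 0.1 × 0.9^5 = 0.886.

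| q | r at p = 10% | P(pass) if counted | P(at least 1 affected in 6) = 1−(1−q)^6 |
|---|---|---|---|
| 0.5% | 0.1045 | 0.877 | 3.0% |
| 1% | 0.109 | 0.868 | 5.9% |
| 2% | 0.118 | 0.849 | 11.4% |

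At q = 1% the loss is 0.012 for p = 5%, 0.018 for p = 10% and 0.020 for p = 20%.

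**The case against.** The best defence is that the plan already has ways to catch such an event. The first discretionary clause of 3.1.9 reaches any exempt event, whether or not the subject is evaluable. Under 3.1.9 the dose decisions rest only primarily on the DLT count. The internal safety panel of 3.1.14 reviews each cohort and can suspend or stop an arm. In an open-label cohort of six, a Grade 3 myocarditis would hardly be missed. All of this stands, and it keeps the point minor. But each route is optional, so the default remains that the event does not count.

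A second defence is that a stopping rule protects the patient while a DLT judges the dose, so the two may differ on purpose. A reader might infer an oversight instead. The documents do not settle it. The amendment history records that Amendment 2 added myocarditis to the pneumonitis bullets of 8.3.1. It also records that Amendment 3 edited 3.1.9 to agree with 8.3.1 on amylase and lipase, with no change for myocarditis. Either reading fits.

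Two stronger readings should be resisted.

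- *The events disappear.* They do not. SAP 9.1.1 plans tables and a listing of events leading to discontinuation, and related Grade 3 or higher events are tabulated.
- *Every stop ordered by 8.3 should be a DLT.* That would also sweep in a first Grade 3 infusion reaction that resolves within 6 hours, and some hepatic events that 3.1.9 exempts. Those exemptions can stand as deliberate choices. Extending the count to them would carry a cost not estimated here.

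SAP 2.2 shortens the DLT definition to any related adverse event, which read literally would count these cases. It gives no grade criteria and is not flagged as a change, so it reads as an abbreviation and not as a planned sensitivity rule.

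**Conclusion.** The mismatch is real but narrow, and its priority is minor. For two event types the default DLT rule is more lenient than the plan's own stopping rule, and in a cohort of six one such event can reverse the decision. A reader might go on to infer that the RCD is unsafe or probably wrong. The documents do not support that. They give no event rates, and Protocol 7.1.8 describes "Myocarditis, a rare, but severe immune-mediated adverse event". The large contrast (0.590 counted against 0.886 replaced or 0.919 scored as no DLT) holds only once an affected subject is in the cohort and other DLTs run at an assumed 10%. Without that condition the difference is about 2 percentage points at an assumed 1% event rate. These figures rest on independent subjects and assumed rates, and on the optional clauses not being used.

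**What to change.** **If dose evaluation is still open:** in criterion 1 of Protocol 3.1.9, list Grade 3 or higher myocarditis and Grade 3 or higher immune nephritis or creatinine elevation (clinically significant, in line with the introduction to 8.3.1) beside pneumonitis. Leave the discretionary clauses and the other exemptions as they are.

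**If dose evaluation is complete:** change only the SAP. Beside the RCD decision, give one sensitivity DLT count that adds the dose-evaluation subjects permanently stopped in Cycles 1 and 2 for these two event types. It cannot undo an RCD already acted on, but it shows whether that RCD depended on the exemption.

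**Cost:** one short protocol edit, or one extra count from data already collected. The downside is that a rapidly reversible event of either type becomes a DLT, so a level is slightly more likely to fail: 0.886 − 0.868 = 0.018, about 2 percentage points at the assumed 1% event rate and 10% other-DLT rate.
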